	12-lead ECG	Subjects must be supine for at least 5 minutes prior to measurement, must be collected at least 15 minutes after the last cigarette smoked.
	Vital signs	Subjects must be seated for at least 5 minutes prior to measurement, must be collected at least 15 minutes after the last cigarette smoked.
	Blood collection for clinical chemistry, hematology, serology, FSH (post- menopausal females) and serum pregnancy test (females)	Blood collection must be preceded by an 8-hour fast.
	Spirometry	To be performed after completion of the assessments listed above, and must be preceded by a minimum 60-minute abstention from cigarette smoking.
	Review of tobacco and nicotine restrictions	
	Smoking cessation information provided	

6.1.2 Baseline and Product Use Period 1

Upon successful completion of Screening, subjects who continue to meet study requirements will be scheduled to check in to the clinic for Test Visit 1 on Day -2 at a time designated by the clinic staff (check-in for JUUL[®] arm should be as early in the day as possible to maximize the time to use the product) and will remain in the clinic until completion of all study events as required by their randomization arm. Reminder telephone calls will be made to the subjects 24 to 48 hours prior to the test visit. Subjects who fail the check-in requirements will be considered a "screen failure" and will be excluded from participation. For the *my*bluTM and continue-smoking arms, the Baseline Period will consist of the time between check-in and first product use on Day 1. The following table provides the general clinic schedule for Test Visit 1. The procedures listed should be performed for subjects as appropriate for the randomization arm.

Time	Procedures	Comments
Day -2		
	Check-in events	
	Urine collection for urinalysis, drug, cotinine, and pregnancy (females) tests Alcohol breath test Exhaled CO measurement	Subjects must have negative drug, alcohol, and pregnancy tests, and have acceptable cotinine and exhaled CO results prior to completing the remaining assessments. Exhaled CO will be measured within 1 hour of check-in.
	Blood sample collection for clinical chemistry and hematology	JUUL [®] arm, following a minimum 8-hour fast.
	Vital signs	Subjects must be seated for at least 5 minutes prior to measurement, must be collected at least 15 minutes after the last study product used.
	Update medical history, and tobacco use history/usual brand cigarette documentation	

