	Document non-compliant tobacco product use and update usual brand cigarette documentation	
	Update AEs and medications	Throughout the day
	Symptom-driven physical examination	
	Body weight documentation	
	Review of in-clinic tobacco and nicotine restrictions	Any time prior to the start of product use
	Subject product use reporting confirmation	Any time prior to discharge
Through 23:00	Product use	
14:00 - 15:00	Start of 24-hour urine collection	
17:00 - 18:00	Blood sample collection for COHb	
20:00 - 22:00	Questionnaires administered (PSCDI/PSECDI, Cough, QSU-Brief, MTWS-R, PES, Product Liking, Future Intent to Use, Product and Health Effects Perceptions)	Subjects must be allowed a period of approximately 2 hours of product use prior to questionnaire administration.
Day 57		
	Document AEs and medications	Throughout the day
	Blood sample collection for clinical chemistry, hematology, and BoPH/bio-banking	Following a minimum 8-hour fast and prior to the start of product use
07:00 - 14:00	Product use	End of product use period will coincide with the end of the 24-hour urine collection
14:00 - 15:00	End of 24-hour urine collection	± 30 minutes from the start time on Day 56

Time*	Procedures	Comments
After urine collection	FeNO	Must be preceded by a minimum 1 hour food and water restriction and a 30 minute abstention from study product use.
After FeNO	Spirometry	Must be preceded by a minimum 60 minute abstention from study product use.
~18:00	Discharge subjects Symptom-driven physical Vital signs 12-lead ECG Provide smoking cessation information Subject cigarettes returned	Discharge events may be completed prior to 18:00. Subjects must be seated for at least 5 minutes prior to vital signs measurement and supine for at least 5 minutes prior to ECG measurement, and both must be collected at least 15 minutes after the last study product used.

* For any procedures to be performed at home, subjects will be instructed to perform these procedures as close to the scheduled times as possible. Subjects will also record the exact clock time of performing the procedures.

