6.2.12 Lung Function (Spirometry)

Subjects will undergo lung function testing at Screening to affirm eligibility (FEV₁, FEV₁:FVC ratio) and as a safety endpoint (FEV₁, FVC, FEV₁:FVC ratio, and forced expiratory flow (FEF)_{25-75%}).

Spirometry measurements will be conducted in accordance with the 2005 American Thoracic Society / European Respiratory Society Joint Task Force on the standardization of spirometry (Miller et al., 2005). The spirometry predicted values will be standardized by the Third National Health and Nutrition Examination Survey predicted set. Personnel performing spirometry tests must receive appropriate training and the spirometer must be kept calibrated as recommended by the manufacturer.

The spirometry tests should be performed in a sitting position following at least 15 minutes of rest and at least 1 hour from the last cigarette smoked or last mybluTM product use. Spirometry must be performed after exhaled CO and FeNO measurements when these events are to be performed on the same day. Multiple measurements may be attempted, but no more than 8 test maneuvers should be performed during a test session. If a subject shows signs of fatigue during repeated testing, testing will be halted and further attempts will only be allowed at the Investigator's discretion.

The subjects will be instructed on how to correctly perform spirometry tests by appropriately trained personnel prior to the measurements being recorded. Spirometry measurements will be performed before and after administration of a short-acting bronchodilator (albuterol). Following acceptable pre-bronchodilator measurements, subjects will be administered 4 puffs

from an albuterol metered-dose inhaler at approximately 30 second intervals (\sim 360 µg total dose assuming 90 µg per puff) using a spacer and a 5-second breath hold after each puff. Post-bronchodilator measurements will be made approximately 10 - 15 minutes following the last albuterol puff.

Each clinic site will be responsible for procuring sufficient supplies to perform the spirometry measurements, including quantities of albuterol and any additional materials for its administration, and for keeping accurate documentation of accountability, dispensing/administration, and disposal of these items as appropriate.

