# 7.7 Electrocardiogram

A single 12-lead electrocardiogram (ECG) will be recorded at Screening for all product arms. For *my*bluTM and continue-smoking arms, the ECG will also be performed at the discharge from the study (Day 57) or upon early termination. For JUUL arm, the ECG will be performed at Day 1 and upon early termination.

Descriptive statistics will be reported for ECG parameters by product arm and time point. Unscheduled events or rechecks post randomization will not be included in summaries. Similarly early termination results will not be included in summaries.

ECG results will be listed by subject.

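### Screening puts the ECG and vital signs before albuterol spirometry, but Table 9 lists them after it on Day 57, so a within-arm reading of the ECG may not be like for like

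*Protocol*

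**What the plan says.** **Screening.** Protocol Table 4 (Section 6.1.1) lists the ECG and vital signs above spirometry, and the comment on spirometry reads "To be performed after completion of the assessments listed above". The order is explicit.

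**Day 57.** Table 9 (Section 6.1.3) runs as follows: the 24-hour urine collection ends between 14:00 and 15:00, FeNO comes next, spirometry comes after FeNO, and discharge at about 18:00 includes vital signs and the 12-lead ECG. Discharge events are allowed to be finished before 18:00. Besides the rest periods, the rule for vital signs and ECG is that "both must be collected at least 15 minutes after the last study product used".

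**Spirometry.** Section 6.2.12 has measurements before and after albuterol: "Following acceptable pre-bronchodilator measurements, subjects will be administered 4 puffs", about 360 µg in total, and then "Post-bronchodilator measurements will be made approximately 10 - 15 minutes following the last albuterol puff". It makes no exception for Day 57, and protocol Section 7.6 summarises both pre- and post-bronchodilator values. Its ordering rule is "Spirometry must be performed after exhaled CO and FeNO measurements when these events are to be performed on the same day". It does not mention the ECG or vital signs.

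**Analysis.** SAP Section 7.7 states "Descriptive statistics will be reported for ECG parameters by product arm and time point" and leaves early-termination results out of the summaries. In the myblu and continue-smoking arms the ECG is scheduled only at Screening and at discharge or early termination.

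**The concern.** Secondary objective 10 is to confirm the safety of myblu over 56 days of use. The ECG evidence for that in the main study is a table with two scheduled time points, which a reader will naturally compare. The first reading is always free of same-visit albuterol. The second, if a site follows the listed order, is taken after a bronchodilator, and nothing controls how long after.

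To the extent that albuterol moves heart rate or the corrected QT, a difference between the two columns could not be attributed to 56 days of product use. The size and direction of such an effect are not in the documents. Section 6.2.11 names Bazett as the rate correction for QT, so an effect on heart rate could also reach the corrected interval. The Day 57 discharge vital signs have the same weakness, but other readings can stand in for them.

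**Working it through.** **Dose.** 4 puffs × 90 µg = 360 µg, which agrees with the protocol's own figure.

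**The two schedules side by side**

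| | Screening (Table 4) | Day 57 (Table 9) |
|---|---|---|
| ECG and vital signs | above spirometry | below spirometry, about 18:00, earlier allowed |
| Spirometry | after everything listed above it | after FeNO |
| Order of ECG and vital signs against albuterol | fixed: before | not stated |
| Interval from albuterol | not needed | none |

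**How far after albuterol the discharge readings could fall.** Inputs: product use stops with the end of the urine collection, at time E (Table 9); spirometry needs 60 minutes without product (Table 9); the four puffs are about 30 seconds apart (Section 6.2.12). Assumptions: the pre-bronchodilator manoeuvres take 10 minutes, and spirometry starts as soon as it may.

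Last puff = E + 60 + 10 + 3 × 0.5 = E + 71.5 minutes. Gap to an 18:00 reading = (18:00 − E) − 71.5.

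- E = 14:00: 240 − 71.5 = 168.5 minutes
- E = 15:00: 180 − 71.5 = 108.5 minutes
- With the ±30-minute urine window, E = 13:30: 270 − 71.5 = 198.5 minutes
- With the same window, E = 15:30: 150 − 71.5 = 78.5 minutes

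A later start to spirometry shortens these gaps. If discharge events directly follow the post-bronchodilator test, the gap is about 10 to 15 minutes. The 5 minutes of supine rest bring it to about 15 to 20 minutes for the ECG. The possible range is therefore roughly 10 to 200 minutes.

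**Are there other readings?** For the ECG, none is scheduled between Screening and discharge. Vital signs are also taken on Days 28, 29 and 56, with no spirometry on those days (Table 2). The heart-rate and blood-pressure endpoints use the check-in readings of Test Visits 1, 3 and 5 (protocol Sections 6.5.2 and 7.4.3), the last on Day 56, before Day 57 spirometry.

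**Which comparison is affected?** Let *a* be the mean albuterol effect on a Day 57 reading, *m* and *s* the albuterol-free Day 57 means in the myblu and continue-smoking arms, and *m₀* the myblu Screening mean.

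- Within arm: (*m* + *a*) − *m₀* = (*m* − *m₀*) + *a*. The effect stays in.
- Between arms: (*m* + *a*) − (*s* + *a*) = *m* − *s*. The effect cancels on average. Uneven gaps add variance only.

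**Can the order be recovered?** The planned listings carry clock times: an albuterol row with its time in the spirometry listing (SAP Appendix 16.2.8.6), and the time of each reading in the vital-sign and ECG listings (Appendices 16.2.8.2 and 16.2.8.3).

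**The case against.** The strongest reply is that no text requires the ECG or vital signs to follow spirometry. Table 9 lets discharge events be done early, and the abstention times leave room: 15 minutes for ECG and vital signs, 30 for FeNO and 60 for spirometry. A site could take the ECG while waiting for spirometry. This stands. The number of affected subjects is unknown and could be anywhere from none to all who reach Day 57. It does not close the gap, because Screening fixes the order and Day 57 leaves it open.

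Second, continue-smoking subjects follow the same Table 9 and receive the same albuterol. This also stands: a reader might infer that the safety comparison with continued smoking is confounded, and on average it is not.

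Third, no change from baseline is planned for the ECG or safety vital signs. SAP Section 7.5 specifies one for laboratory data, whereas Sections 7.6 and 7.7 give descriptive statistics by arm and time point. So no planned statistic is biased. What suffers is the reading that a two-time-point table invites.

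Two further inferences are tempting and not supported. One is that albuterol would be invisible in the data because Section 6.2.3 exempts it from medication recording. The spirometry listing shows it, with its time. The other is that the JUUL column is made non-comparable. That arm has no spirometry with its Day 1 ECG, but no ECG comparison with it is planned, and its ECG follows use only from Day -2 to Day 1, not 56 days.

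**Conclusion.** The point holds as an unreconciled order of measurements. Where a site follows Table 9 as listed, the only scheduled and summarised post-Screening ECG in the two main-study arms falls somewhere between about 15 and 200 minutes after about 360 µg of albuterol. Set against an albuterol-free Screening ECG, it is not like for like. The same applies to the Day 57 discharge vital signs, with less consequence because Days 28, 29 and 56 give readings without same-day spirometry and the heart-rate and blood-pressure endpoints use check-in values.

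The timing range rests on the assumed 10 minutes of manoeuvres and the earliest permitted start of spirometry. Balance between the arms rests on sites using the same order in both and on albuterol acting alike in both. A reader might want to attach a number of beats per minute or a QT shift in milliseconds. The documents give neither the size nor the duration of any albuterol effect, so no such figure can be supported. The primary endpoints, the sample size and the planned inferential tests are unaffected.

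**What to change.** Reconcile Table 9 with Table 4: list the Day 57 discharge vital signs and ECG above spirometry. Extend the same-day ordering sentence in Section 6.2.12 so that spirometry also follows the ECG and vital signs. The readings fit into the 60-minute wait that spirometry already imposes. The cost is two rows moved, one sentence changed, and a little less scheduling freedom for sites on Day 57. No procedure or visit is added.

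For data already collected, compare the albuterol time in the spirometry listing with the times in the ECG and vital-sign listings. Flag each Day 57 reading taken after albuterol, and footnote SAP Tables 14.3.5.4 (vital signs) and 14.3.5.5 (ECG) with the number flagged in each arm. This uses only fields already in the planned listings.

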6.1.4 Follow-up Period

All subjects will be contacted by telephone 14 days (± 2 days) following discharge from the study on Day 57 (or following early termination if deemed necessary in the opinion of the Investigator) to document the occurrence of AEs and the need for concomitant medications since the last clinic visit. The Investigator will determine whether additional follow-up will be necessary based on the outcome of this call.

6.2 Study Events

6.2.1 Medical History

Medical history is defined as any condition that started prior to Day -2. Relevant medical history, as determined by the Investigator or a qualified designee, will be documented at Screening and updated at Test Visit 1 as necessary.

6.2.2 Demographics

Basic demographic data and subject identification information, including sex, age (each subject must show proof of age with government-issued identification (ID) [e.g., driver's license]), race, and ethnicity will be recorded for each subject at Screening.

Additional demographic data, including income level, educational level, marital status, and gender choice (if self-determined to be different from sex), will be obtained during Test Visit 1.

The demographics questionnaires are located in Appendix 1.

6.2.3 Prior and Concomitant Medications

Any prior and concomitant medications (with the exception of albuterol used during spirometry measurements) taken from 30 days prior to Screening through the Follow-up Period will be recorded. Subjects will be advised to report regular use of medications to the clinic staff as the need arises during the ambulatory periods. Occasional use of medications during the ambulatory periods may be reported at the next Test Visit. Details to be recorded include the drug name (generic and trade name if applicable), route of administration, total dose/unit, indication, start date, and stop date. Prior and concomitant medications will be coded using the World Health Organization (WHO) Drug Dictionary.

6.2.4 Smoking History and Usual Brand Combustible Cigarette Documentation

Smoking history will include the number of years the subject has smoked and the average number of cigarettes (single value, not a range) smoked per day during the past year.

In addition, a color photocopy of each subject's usual brand cigarette package will be obtained initially at the Screening. An updated photocopy will be taken and product characteristics documented if the subject's usual brand changes during the study. The following characteristics of the usual brand product will be documented: brand, brand style, flavor, and cigarette length. A data collection form will be provided to the site.

6.2.5 Tobacco/Nicotine Product Use History Questionnaire

Subjects will be required to report previous tobacco-product and nicotine-product use histories during Screening and updated at Check-in for Test Visit 1 (if necessary) to satisfy the study inclusion and exclusion criteria.

The Tobacco/Nicotine Product Use History Questionnaire is provided in Appendix 12.

6.2.6 Physical Examination

A standard physical examination assessing the general physical well-being will be performed at Screening. A symptom-driven physical examination will be conducted at other times to evaluate AEs. If no symptoms are present, an examination will not be required.

6.2.7 Body Weight, Height, and BMI

Body weight will be measured in light indoor clothing during Screening and Test Visits 1, 3 and 5. Height and BMI will be documented during Screening. Measurements will be reported in metric units. BMI will be recorded as kg/m^2 .

6.2.8 Clinical Laboratory Tests

All clinical laboratory tests will be conducted by a central laboratory facility accredited by the Centers for Medicare and Medicaid Services (Clinical Laboratory Improvement Amendments of 1988 [CLIA-88]) or at the clinic site. For inclusion into the study, values for the clinical laboratory parameters are to be within the laboratory normal ranges or deemed not clinically significant in the opinion of the Investigator.

Clinical Chemistry¹

- Albumin
- Alkaline phosphatase
- Alanine aminotransferase
- Aspartate
- aminotransferaseBicarbonate
- BicarbonaBilirubin
- Blood urea nitrogen
- Creatinine
- Glucose
- Potassium
- Sodium
- Total protein
- Uric acid

Hematology

- Hematocrit
- Hemoglobin
- Platelet count
- Red blood cell count
- White blood cell count with differential
- ¹ Clinical chemistry tests will be performed after a minimum 8-hour fast; however, in case of dropouts or rechecks, subjects may not have fasted for 8 hours prior to the serum chemistry sample is taken and test results will be interpreted appropriately.
- ² A microscopic examination for red blood cells, white blood cells, bacteria, and casts will be performed if an abnormality is noted in leukocyte esterase, protein, blood, or nitrite.
- ³ Human chorionic gonadotropin (females only).
- ⁴ NicAlert, Accutest Urine Cotinine Test, or other screening kit providing real-time results with a similar level of sensitivity. The same type of kit will be used at each site.

6.2.9 Exhaled Carbon Monoxide

Exhaled CO levels will be measured using a Bedfont Micro+ Smokerlyzer, or similar device, within 2 hours of presentation to the study site at the Screening Visit and within 1 hour of presentation to the site at other Test Visits where noted. Measurements will be used to confirm eligibility prior to randomization and will be used as a measure of compliance

Urinalysis²

- Bilirubin
- Blood
- Glucose
- Ketones
- Leukocyte esterase
- Nitrite
- pH
- Protein
- Specific gravity
- Urobilinogen

Additional Tests

- Serology
- o HIV
- o HbsAg
- o HCV
- FSH
- Serum/urine pregnancy ³
- Urine cotinine ⁴
 - Urine drug test
 - Amphetamines
 - Cannabinoids
 - Cocaine
 - \circ Methamphetamine
 - Opiates
- Alcohol breath test

thereafter. Subjects may be provided their results during compliance discussions to demonstrate compliance/noncompliance.

6.2.10 Vital Signs

Vital signs (respiratory rate, heart rate, blood pressure, and oral temperature) will be measured at Screening, check-in and discharge for Test Visits 1, 3, and 5. Measurements will be taken after the subject has been in a seated position for at least 5 minutes and at least 15 minutes after the last cigarette smoked or study product used.

6.2.11 Electrocardiogram

12-lead ECGs will be taken following resting in the supine position for at least 5 minutes and at least 15 minutes after the last cigarette smoked or study product used during Screening and at discharge from the study. ECGs will be interpreted, signed, and dated by the Investigator or a qualified designee. Clinic site reference ranges will be applied to all ECG parameters. The ECG machine will compute the PR and QT intervals, QT interval corrected for heart rate using Bazett's (QTcB) formula, QRS duration, and heart rate and this information will be documented in the subject file. The ECGs will be interpreted as normal, having a clinically insignificant abnormality, or having a clinically significant abnormality. The overall interpretation will be noted in the eCRF.

6.2.12 Lung Function (Spirometry)

Subjects will undergo lung function testing at Screening to affirm eligibility (FEV₁, FEV₁:FVC ratio) and as a safety endpoint (FEV₁, FVC, FEV₁:FVC ratio, and forced expiratory flow (FEF)_{25-75%}).

Spirometry measurements will be conducted in accordance with the 2005 American Thoracic Society / European Respiratory Society Joint Task Force on the standardization of spirometry (Miller et al., 2005). The spirometry predicted values will be standardized by the Third National Health and Nutrition Examination Survey predicted set. Personnel performing spirometry tests must receive appropriate training and the spirometer must be kept calibrated as recommended by the manufacturer.

The spirometry tests should be performed in a sitting position following at least 15 minutes of rest and at least 1 hour from the last cigarette smoked or last mybluTM product use. Spirometry must be performed after exhaled CO and FeNO measurements when these events are to be performed on the same day. Multiple measurements may be attempted, but no more than 8 test maneuvers should be performed during a test session. If a subject shows signs of fatigue during repeated testing, testing will be halted and further attempts will only be allowed at the Investigator's discretion.

The subjects will be instructed on how to correctly perform spirometry tests by appropriately trained personnel prior to the measurements being recorded. Spirometry measurements will be performed before and after administration of a short-acting bronchodilator (albuterol). Following acceptable pre-bronchodilator measurements, subjects will be administered 4 puffs

from an albuterol metered-dose inhaler at approximately 30 second intervals (\sim 360 µg total dose assuming 90 µg per puff) using a spacer and a 5-second breath hold after each puff. Post-bronchodilator measurements will be made approximately 10 - 15 minutes following the last albuterol puff.

Each clinic site will be responsible for procuring sufficient supplies to perform the spirometry measurements, including quantities of albuterol and any additional materials for its administration, and for keeping accurate documentation of accountability, dispensing/administration, and disposal of these items as appropriate.

